Apathy, which is defined as the loss or reduction of interest and goal-directed behaviors, is the most common NPS in ADRD, with a 5-year prevalence over 70% in this population (7, 8). Apathy has been associated with greater functional impairment, greater caregiver burden, increased risk of institutionalization and higher costs (9, 10). Because of its prevalence and clinical meaning, apathy is an important target in the management of ADRD. Standard pharmacological approach for apathy in ADRD uses cholinesterase inhibitors such as donepezil, with evidence of either no or very small effectiveness (10, 11). The stimulant methylphenidate was also shown to be effective in reducing apathy in ADRD in open studies and two double-blind randomized controlled trials (12). However, the use of methylphenidate was associated not only with reduction in apathy but also with greater anxiety and weight loss (13). Another concern with the use of stimulants is their potential cardiovascular effects, a fact particularly relevant in older adults with multiple medical comorbidities (14). Studies investigating non-pharmacological strategies for apathy in ADRD, such as music, art therapy and psychomotor activity, have modest effects and only in patients in early stages of dementia (15). Therefore, there is a great need to develop effective and safe strategies for the treatment of apathy in ADRD.

Transcranial direct current stimulation (tDCS) is a relatively novel non-pharmacological method of neuromodulation that has been evaluated in several neuropsychiatric conditions, showing promising results in depression and negative symptoms (including apathy) of schizophrenia (16, 17). tDCS modulates brain activity through low-intensity electrical currents applied over the scalp, and has been associated with significant changes in network connectivity involving the prefrontal cortex and the cingulate cortex, regions implicated in the neural basis of apathy (18-20).

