We will carry out a randomized, experimenter- and participant-blinded trial comparing home-based active tDCS and home-based sham tDCS. Participants will be randomized 1:1 to either treatment condition. Half of the participants (n=20) will receive active (constant current intensity of 2mA), while half (n=20) will receive sham tDCS. No changes to the patient's standard care medication will be made. Participants will continue to receive standard treatment for their individual health problems. **Anode and cathode electrodes will be placed over the left and right dorsolateral prefrontal cortices, respectively, with the use of the Omni-Lateral-Electrode system.** Caregivers will set up and administer tDCS for participants with ADRD at home. tDCS will be applied for 30 min at an intensity of 2mA, with 30 s ramping up and down. The same procedure will be used for sham stimulation, but in this case, electric current will be applied only in the first 30s tDCS. All patients, caregivers and clinicians will be blinded to the type of stimulation delivered. We will use bi-hemispheric stimulation (anode F3/cathode F4) based on the facts that bilateral frontal circuits have been implicated in apathy, and bilateral stimulation may have wider effects on brain networks (18, 23, 26). The stimulation will last 30 min according to previous studies (17, 23, 27). According to our previous home-based tDCS protocols (28, 29), all sessions will be remotely supervised by trained research staff (RA), therefore, the sessions will run from Monday to Friday. The remote supervision of the sessions will be possible through video conferencing software (e.g., WebEx), and will ensure the use of proper technique and compliance to the study schedule, also monitoring any adverse events (Fig.1). The devices (tDCS & sham tDCS) will be programmed and cannot be tampered. Participants will be assessed at baseline,

[figure not shown]
[figure not shown]

Fig. 1 Illustrative image of home-based tDCS.

treatment day 14, treatment day 28, treatment day 42, and 6 weeks post-treatment (Fig. 2). The device will be returned in person at the end of the treatment (week 6).

Fig. 2 Proposed outline of the study.

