Inclusion criteria will be: (1) diagnosis of possible or probable ADRD according to the National Institute of Aging – Alzheimer’s Association diagnostic criteria (34); (2) mild or moderate dementia, **as defined by a MMSE score between 14 and 26** (35, 36); (3) clinically meaningful apathy for at least four weeks, clinically diagnosed according to 2018 Apathy Diagnostic Criteria (37) or defined as Neuropsychiatric Inventory (**NPI-Q**) apathy score equal or above 4 (i.e., severity of ‘moderate’ or greater **and caregiver distress ‘mild or greater’** (38-40); (4) stable doses of cholinesterase inhibitors, memantine and other psychotropic medications for at least three months.

Exclusion criteria will be: (1) unstable medical conditions; (2) history of epilepsy; (3) metallic objects in the brain; (4) diagnosis of major depression and/or a score higher than 18 on the Cornell Scale for Depression in Dementia (41).

Recruitment and Retention. Subjects will be recruited at the *UTHealth Geriatric Neuropsychiatry Clinic, the Harris County Psychiatric Center (HCPC)* ([name]) and the *UT Physicians Center for Healthy Aging* ([name]). As serious adverse effects and problems with the device use are not anticipated, it is expected a high retention rate. The remote supervision of the tDCS or tDCS sham daily sessions by trained research staff will contribute to the retention of subjects during the trial.

Training plan. Patients will be instructed on treatment at baseline, when they will receive the device. A trained research staff will instruct the participant's caregiver on how to handle the equipment. All sessions will be remotely supervised by trained research (RA) staff, who will be able to answer questions during the sessions and verify that the device is being used correctly.

Study Procedures

Feasibility measures will include recruitment rate (per month), randomization success, blind success, retention and attrition rates. Overall consent and completion rates will be evaluated via descriptive statistics. Generalized linear modeling (GLM) will evaluate treatment group differences in consent and completion rates. We expect that a high proportion of participants will consent to participate (> 80%) and complete the study (> 70%).

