Acceptability will be evaluated using the method proposed by Ahn et al. (2019) (29). Participants and/or their caretakers will be asked to apply a Likert scale (from 0 [strongly disagree] to 10 [strongly agree]) to answer ten affirmatives regarding the use of home-based tDCS. For example, question 1: "It was easy to prepare the device and accessories", question 7: "I felt confident using the device." Overall acceptability across groups will be evaluated by descriptive measures of satisfaction ratings. GLM will model participant satisfaction ratings as a function of treatment group (active vs. sham tDCS). We expect that participant satisfaction ratings at the end of treatment will demonstrate high acceptance of tDCS treatment in the present sample.

Safety will be assessed with a questionnaire about side effects that include itching, burning, headache, fatigue, and dizziness (29). Descriptive statistics will describe raw frequencies of AEs and side effects. Treatment group differences in AEs and side effects will be evaluated via Chi-square and Fisher's exact test of contingency tables. We expect that adverse events and side effects will be rare, and any that may occur will be mild.

The primary clinical outcome measure will be change on the Apathy Evaluation Scale score (42), the best-validated scale for measuring apathy in AD, which consists of 18 items phrased as questions that are to be answered by the caregiver on a four-point Likert scale, with higher scores indicating greater severity of apathy. Apathy will be

assessed at baseline, during treatment (weeks 2, 4 and 6) and 6 weeks post-treatment. Our hypothesis is that active tDCS group will demonstrate lower apathy scores at the end of treatment relative to sham tDCS. GLM will evaluate residual change by modeling apathy at the end of treatment as a function of treatment group, controlling for apathy at the beginning of treatment. This analysis is a regression-based analogue to ANCOVA that permits non-normally distributed outcome distributions. Follow-up analyses will evaluate change over time across groups via GLM with multilevel components (GLMM) as well as cross-sectional analyses within each measurement time point via GLM.

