The secondary clinical outcome measures will include: (1) total score on the Brief Dimensional Apathy Scale (bDAS) (43); (2) total score on the NPI-Q which evaluates 12 discrete NPS considering their severity and the related caregiver distress (38-40); (3) depressive symptoms as assessed by the Cornell Scale for Depression in Dementia (41); (4) cognition as evaluated by the Mini-Mental State Examination (MMSE), which includes memory, language, praxis and orientation tasks, yielding a global cognition score ranging 0 to 30, with higher scores indicating better performance (35).

Our hypothesis is that active tDCS group will demonstrate lower scores on the bDAS, NPI-Q and Cornell Scale for Depression, and higher scores on the MMSE at the end of treatment relative to sham tDCS. GLM will evaluate residual change in each outcome (in separate models) by modeling scores at the end of treatment as a function of treatment group, controlling for baseline.

Sociodemographic data (gender, age, marital status and education) will be collected at the baseline. Clinical (health history, use of medication and life habits) and anthropometric data will be collected at the baseline and after the treatment period. These data will be control variables for the study.

Table 1. Timetable for Collection of Data

Assessment	Baseline	Week 2	Week 4	Week 6	Week 12
Medical History Questionnaire	X				
MMSE	X			X	X
AES (primary outcome)	X	X	X	X	X
NPI-Q	X	X	X	X	X
bDAS	X	X	X	X	X
Cornell Scale for Depression	X			X	X
tDCS experience questionnaire		X	X	X	X
Side effects questionnaire		X	X	X	X

Data and Safety Monitoring

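### The NPI-Q total includes the apathy that treatment targets, so it can hide worsening of other symptoms, and no planned safety analysis ensures that such worsening is seen

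*Combined protocol and SAP*

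**What the plan says.** Safety stands with feasibility and acceptability in the primary objective (General Information; Objectives). In Study Procedures, the safety paragraph reads: "Safety will be assessed with a questionnaire about side effects that include itching, burning, headache, fatigue, and dizziness". It continues: "Descriptive statistics will describe raw frequencies of AEs and side effects", and "Treatment group differences in AEs and side effects will be evaluated via Chi-square", with Fisher's exact test named as well. Study Design adds that staff supervise every session by video, "also monitoring any adverse events".

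The secondary clinical outcomes in the same section include the "total score on the NPI-Q which evaluates 12 discrete NPS considering their severity and the related caregiver distress", together with the Cornell depression scale and the MMSE. The hypothesis for all of them is benefit. Each has its own model: the end-of-treatment score by group, adjusted for baseline.

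Table 1 schedules the NPI-Q at baseline and weeks 2, 4, 6 and 12, and Cornell and MMSE at baseline and weeks 6 and 12. That apathy is an NPI-Q item follows from the inclusion criteria, where one entry route is an NPI-Q "apathy score equal or above 4".

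**The concern.** A total over 12 symptoms that includes the treatment target mixes benefit with possible harm. If stimulation lowers apathy and also provokes another symptom, the two movements offset each other in the NPI-Q total. The Background describes this pattern for a drug: "the use of methylphenidate was associated not only with reduction in apathy but also with greater anxiety and weight loss".

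The safety paragraph does not clearly fill the gap, because none of the side effects it names concerns mood, behaviour or cognition. The pilot could report a stable or lower NPI-Q total and few, mild side effects while worsening of individual symptoms went unexamined. The publication plan intends the results to guide adjustment or expansion of the protocol, so this would matter. The data needed to look are already scheduled.

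**Working it through.** **The plan's own figures.** The documents give no figure for safety or for the NPI-Q. The only sample-size figure is 80% power at N = 40, alpha 0.05 and Cohen's f = 0.45. It reproduces: noncentral F with 1 and 37 degrees of freedom and noncentrality 0.45² × 40 = 8.1 gives 79.1%. It does not bear on this point.

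**Offset within the total.** The documents do not set out the NPI-Q scoring. The inclusion criteria explain the apathy score of 4 through both severity and caregiver distress, so I assume that each item is severity plus distress and that items are summed.

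- One participant: apathy 4 to 0 and anxiety 0 to 4 gives a total change of −4 + 4 = 0.
- Active-arm mean: let A be the mean apathy fall, p the proportion with a new symptom and s its score. Net change = −A + p × s, which is zero when p = A/s. If sham does not change, this is also the between-arm difference.

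| A | s | p | Net change |
|---|---|---|---|
| 1 | 4 | 25% | 0 |
| 1 | 2 | 25% | −0.5 |
| 1 | 2 | 50% | 0 |
| 2 | 4 | 25% | −1.0 |
| 2 | 4 | 50% | 0 |

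A, s and p are illustrative, since the documents give no rates. In the second and fourth rows the total improves although a quarter of the arm has a new symptom.

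**Visits used.** End of treatment is week 6. Of four post-baseline NPI-Q assessments, the stated model uses one. The follow-up analyses over time and by visit are described for the apathy outcome.

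**The adverse-event route.** Sessions last 30 minutes on five days a week: 2.5 of 168 hours, or 1.5% of the week. The documents do not define an adverse event, do not say how events between sessions are elicited, and do not say when a worse NPI-Q, Cornell or MMSE score becomes one. The Data and Safety Monitoring section covers data storage, confidentiality and sharing.

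**What a by-arm count could show.** Power of the two-sided Fisher test at 0.05, with assumed rates. The 14 per arm is 70% of 20, the protocol's completion expectation at its limit.

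| Active vs sham | 20 per arm | 14 per arm |
|---|---|---|
| 20% vs 5% | 17% | 7% |
| 30% vs 10% | 24% | 14% |
| 40% vs 10% | 49% | 32% |
| 50% vs 10% | 74% | 54% |

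The chance of seeing at least one case among 20 active participants is 1 − (1 − rate)^20: 64% at a true rate of 5%, 88% at 10% and 99% at 20%. With 0 of 20, the one-sided 95% upper bound is 1 − 0.05^(1/20) = 13.9%. Such counts describe; they do not test.

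**Why by item.** Eleven non-apathy items at weeks 2, 4 and 6 give 33 chances to be flagged. With independent background fluctuation of 5% per item and visit, 1 − 0.95^33 = 82% of participants in either arm would have some worse item; at 1% it is 28%. A count of any worse item could therefore be close to saturated in both arms.

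**The case against.** The strongest reply is that safety is not limited to the questionnaire. Adverse events are monitored throughout each session, counted and tested by arm, and the side-effect form is also given at weeks 2 and 4. A reader might infer that new agitation or anxiety can never reach the safety result, or that a symptom present at week 2 and gone by week 6 leaves no trace. The documents do not support either reading: such a symptom recorded as an adverse event would be tabulated. The Statistics section also promises descriptive statistics for all measured variables, which would cover the early NPI-Q data in some form. The list of side effects is open, so the form itself may hold more items than are named. What remains is that no rule or named analysis ensures capture, and no item-level summary by arm is specified.

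A reader might also infer that the masking extends to depression on the Cornell scale or decline on the MMSE. It does not. Each has its own model, so an NPI-Q apathy gain cannot offset either. A hypothesis of benefit does not itself conceal harm, because the Bayesian analysis considers effects in both directions. The narrower point for these two scales is that a group mean can hide individual worsening.

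Finally, anxiety on a stimulant drug is not evidence about tDCS, and the Background reports the one earlier tDCS trial of these symptoms in dementia as safe. That is fair. The drug example shows that the pattern is plausible, not that it is expected here.

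**Conclusion.** The point holds, confined to the NPI-Q total and to the lack of a planned link from that scale to safety. The total includes the targeted symptom, its stated model uses one of four post-baseline assessments, and no specified analysis separates worsening elsewhere from apathy improvement.

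That offset is possible follows from the structure of the score. Its size does not: the 25% and 50% break-even proportions rest on assumed severity-plus-distress scoring, a new symptom scored 4, and an unchanged sham arm. The documents give no basis for saying that harm is likely, or that it would certainly be missed. This is a gap in how a primary objective is analysed, and it can be closed with data already scheduled.

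**What to change.** In the safety paragraph of Study Procedures, add by arm and descriptively:

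1. For each NPI-Q item other than apathy, the number of participants new or worse than baseline at weeks 2, 4, 6 and 12. List by item; do not make a count of any worse item the main summary.
2. The distribution of individual change from baseline in Cornell and MMSE at weeks 6 and 12, showing the participants who worsened. Do not count crossings of the entry limits, because these depend on baseline. With the Cornell exclusion ("a score higher than 18 on the Cornell Scale for Depression in Dementia") as cut-off, 18 to 19 would count and 2 to 18 would not. With the MMSE floor of 14, a participant entering at 14 is flagged after losing one point, while one entering at 26 can lose 12 and not be flagged.

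In the secondary-outcome paragraph, report the NPI-Q total without the apathy item beside the full total, using the same baseline-adjusted model.

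The cost is a few more tables, with no new visit, scale or staff. Some background fluctuation will be counted in both arms, and between-arm tests have low power with 20 per arm, so the counts should be presented as descriptive.

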
sham tDCS), and specified outcome variables (e.g., Apathy) via traditional statistical tests (e.g., chi-square; Mann-Whitney; *t*-tests). Any sample characteristic variables that demonstrate a relationship with both predictor and outcome variables in a given model meet criteria for being a potential confounder (32, 33) and will be included as a covariate in such models for hypothesis testing.

Statistical modeling will primarily use generalized linear modeling (GLM) with multilevel components (GLMM) for correlated observations. Potentially nonlinear relationships between predictors and outcomes will be evaluated via inclusion of polynomial or spline effects. Continuous, dichotomous, and count-distributed data will utilize linear, logistic, and Poisson/negative binomial regression, respectively (each with a canonical link function). Evaluation of distributional assumptions will use residual plots, formal statistical tests, and posterior predictive checking. Violations of assumptions will be addressed via transformation, robust estimation, stratification, and/or coefficient scaling where appropriate. Statistical analyses will be performed using the R statistical computing environment via packages lme, rstan, and brms.

Missing data will be addressed via maximum likelihood, explicit modeling of missingness, or imputation where appropriate. Each approach is robust to ignorable missingness (i.e. MCAR and MAR). Sensitivity analyses will permit evaluation of the robustness of findings to missing data assumptions. While Bayesian analyses are not influenced by traditional concerns of multiplicity, for the frequentist analyses, all primary outcome variables (those specified by name in the hypothesis statements) will be evaluated at the $\alpha = 0.05$ statistical significance level, while any secondary or otherwise post hoc analyses will employ false discovery rate (FDR) to control for Type I error.

Study Population

We will randomize 40 patients aged 60 or older with ADRD and apathy to either active home-based daily (Monday to Friday) tDCS or sham tDCS for 6 weeks (1:1 for two groups). This sample size is set to maximize the number of participants that may be enrolled over the time period of the proposal assuming a credible average recruitment rate, given the financial parameters of the funding mechanism.

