Inferential Paradigm and Bayesian Analyses. Following recommendations in the clinical trial literature analyses we will proceed using parallel frequentist and Bayesian statistical inference (30, 31). The Bayesian inferential paradigm can provide probabilistic estimates of effects irrespective of sample size. Bayesian analyses will focus on posterior probabilities ≥ 0.75 (equivalent to a Bayes factor = 0.33 or 3.0) that parameter estimates are greater or less than zero to emphasize the value in discerning treatment effects in a small trial. Power calculations for the frequentist analyses are derived using G*Power v. 3.1.9.2 and focus on the residual change model described in Hypothesis 2a. As noted, the Bayesian analyses will provide the primary inferential results; sample size considerations for the frequentist analyses are limited by the small sample size and provided as due diligence. Given alpha = 0.05, a sample size N = 40 provides 80% power to detect a Cohen's $f = 0.45$. Frequentist analyses will provide conventional interpretation of the relationships between predictors and outcomes: the probability of the data, given the null hypothesis. Bayesian analyses will incrementally update specified prior information regarding effects to directly yield the probability of an alternative hypothesis. Bayesian analyses will employ informative priors as they develop in the literature; otherwise, weakly informative priors will be used as a default (e.g., for regression coefficients: $\sim N[\mu=0, \sigma^2=100]$; for non-linear outcome variables this prior applies to the coefficient within the link-function). Sensitivity analyses using optimistic and pessimistic, skeptical priors will evaluate prior assumptions. Assessing the convergence of Bayesian analyses on the posterior distributions via Monte-Carlo Markov chain (MCMC) will use diagnostic evidence including effective sample size and scale reduction factors.

Evaluation of posterior distributions will permit statements regarding the probability that effects of varying magnitudes exist, given the data, even with a small sample size.

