Descriptive statistics will evaluate measures of central tendency and frequencies for all continuous and categorical variables (respectively) measured in the study. Correlation analyses (i.e., Pearson's r , Spearman's ρ) will be used to evaluate broad patterns of relationships across variables. Preliminary data analyses will inspect relationships between sample characteristics (e.g., demographics), experimental group (e.g., active vs. sham tDCS), and specified outcome variables (e.g., Apathy) via traditional statistical tests (e.g., chi-square; Mann-Whitney; t -tests). Any sample characteristic variables that demonstrate a relationship with both predictor and outcome variables in a given model meet criteria for being a potential confounder (32, 33) and will be included as a covariate in such models for hypothesis testing.

Statistical modeling will primarily use generalized linear modeling (GLM) with multilevel components (GLMM) for correlated observations. Potentially nonlinear relationships between predictors and outcomes will be evaluated via inclusion of polynomial or spline effects. Continuous, dichotomous, and count-distributed data will utilize linear, logistic, and Poisson/negative binomial regression, respectively (each with a canonical link function). Evaluation of distributional assumptions will use residual plots, formal statistical tests, and posterior predictive checking. Violations of assumptions will be addressed via transformation, robust estimation, stratification, and/or coefficient scaling where appropriate. Statistical analyses will be performed using the R statistical computing environment via packages lme, rstan, and brms.

Missing data will be addressed via maximum likelihood, explicit modeling of missingness, or imputation where appropriate. Each approach is robust to ignorable missingness (i.e. MCAR and MAR). Sensitivity analyses will permit evaluation of the robustness of findings to missing data assumptions. While Bayesian analyses are not influenced by traditional concerns of multiplicity, for the frequentist analyses, all primary outcome variables (those specified by name in the hypothesis statements) will be evaluated at the $\alpha = 0.05$ statistical significance level, while any secondary or otherwise post hoc analyses will employ false discovery rate (FDR) to control for Type I error.

Ethics/Protection of Patient Confidentiality

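### Covariates in the efficacy models are neither limited to pre-randomisation values nor fixed in advance; a screen on arm and outcome decides what enters

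*Combined protocol and SAP*

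**What the plan says.** The primary clinical outcome model for the Apathy Evaluation Scale (AES), under Study Procedures, is "modeling apathy at the end of treatment as a function of treatment group, controlling for apathy at the beginning of treatment". Each secondary efficacy model likewise fixes one covariate, the baseline value of its own outcome.

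Further covariates come from two other places.

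- **Study Procedures, paragraph before Table 1.** Sociodemographic data are taken at baseline. Clinical data (health history, medication, life habits) and "anthropometric data will be collected at the baseline and after the treatment period. These data will be control variables for the study". No time point or model is attached to that last statement.
- **Analyses (under Study Design), repeated in Statistics.** "Any sample characteristic variables that demonstrate a relationship with both predictor and outcome variables in a given model" are said to "meet criteria for being a potential confounder (32, 33) and will be included as a covariate in such models for hypothesis testing". No significance threshold, closed list or time-point limit is given.

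Table 1 shows the "Medical History Questionnaire" at baseline only. It has no row for post-treatment clinical or anthropometric data.

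On inference, the Statistics section states: "As noted, the Bayesian analyses will provide the primary inferential results".

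**The concern.** There are two separate problems.

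**Post-treatment values.** Read literally, the paragraph before Table 1 makes values measured after treatment into control variables. If active stimulation changes such a variable and the variable relates to apathy, adjusting for it removes part of the treatment effect. If the variable and the outcome share an unmeasured cause, adjusting for it creates bias even when treatment does nothing to apathy. In both cases the coefficient no longer estimates the effect of assignment to active tDCS. The same model feeds the Bayesian posterior, so the primary inference inherits the error.

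**The screen.** Arm is randomised, so a baseline variable can be related to arm only by chance. A rule that requires an association with arm picks chance imbalances and leaves out prognostic variables that happen to be balanced. Applied to post-treatment variables, it preferentially picks those that treatment has moved. With no threshold stated, the choice is left to the analyst after the outcome data are seen.

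The two texts also disagree on what enters: all of these data in one place, only those that pass the screen in the other.

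**Working it through.** **The plan's own figure.** The Statistics section says: "Given alpha = 0.05, a sample size N = 40 provides 80% power" for Cohen's f = 0.45. For two equal groups d = 2f = 0.90. With noncentrality λ = f²N = 0.45² × 40 = 8.1, numerator df 1, denominator df 37 (two groups, one covariate) and a two-sided test, power is 0.791. The stated 80% reproduces.

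**Set-up for the covariate rules.** From the plan: N = 40, 20 per arm, alpha 0.05, ANCOVA with baseline score. Assumed, because the plan gives no values: baseline correlation 0.5, path strengths, screen thresholds and, where used, the number of candidates. Effects are in units of the outcome's residual SD given arm and baseline. The screen is a t-test of the variable by arm plus a Pearson correlation with outcome, both below the threshold. Simulated power without extra covariates is 78%, slightly under 79.1% because chance baseline imbalance is included.

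**Mediator, true total effect 0.90.** Treatment shifts the variable by *s*, and the variable has slope *b* on the outcome. Always adjusting leaves the direct effect, 0.90 − *s* × *b*:

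- small: 0.90 − 0.3 × 0.3 = 0.81
- mild: 0.90 − 0.5 × 0.3 = 0.75
- half mediated: 0.90 − 0.8 × 0.56 = 0.45

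The screening rule falls between this and no adjustment, depending on how often the variable is selected (20,000 trials per case). Entries are mean estimate / power.

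| Path | Selected, p<0.05 | Rule, p<0.05 | Rule, p<0.20 | Always adjusted |
|---|---|---|---|---|
| Small | 10% | 0.87 / 75% | 0.83 / 72% | 0.81 / 71% |
| Mild | 23% | 0.83 / 71% | 0.78 / 65% | 0.75 / 63% |
| Half mediated | 68% | 0.53 / 40% | 0.47 / 33% | 0.45 / 33% |

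**Posterior probability ≥ 0.75 criterion** (flat-prior approximation, p<0.05 screen). At effect 0.90 it is met in 98% of trials unadjusted, and in 98%, 97% and 85% under the rule for the three paths. At effect 0.50 it is met in 81–82% unadjusted, 79% (small) and 76% (mild).

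**No treatment effect, shared unmeasured cause** (shift 0.3 to 0.8, correlation 0.30 to 0.44).

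| | Two-sided type I error |
|---|---|
| Rule, p<0.05 | 5–11% |
| Rule, p<0.20 | 5–17% |
| Always adjusted | 6–20% |

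Without bias, the posterior passes 0.75 in a given direction in 25% of null trials. In the biased direction, under the p<0.05 rule, this becomes 27–49%.

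**Baseline values only** (8 candidates, 2 prognostic, p<0.05 screen, effect 0.90). Type I error is 4–5%, and power under the screen is 77–78%. With the two prognostic covariates fixed in advance, power is 79%, 84% or 90% at partial r of 0.2, 0.3 or 0.4. If the two have no prognostic value, fixing them gives 76% against 78% with baseline score alone.

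A second simulation with all 8 baseline covariates weakly prognostic and screens at p<0.05 to p<0.20 put the screen's type I error at 2–5%. On baseline values the rule tends to be conservative, not inflating.

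**The case against.** The strongest reply is that baseline values are meant. The Study Design entry in the General Information table places clinical and demographic data at baseline, and Table 1 agrees. The screening rule speaks of sample characteristics, with demographics as its example, and the titles of the two references it cites concern baseline data. No sentence sends a post-treatment value through the screen; that follows only from reading two sections together. This stands as a fair account of the probable intent, and if Table 1 is complete the mediator problem falls away. But demographics is given as an example and not as a limit, and the sentence on control variables comes directly after one that places collection after treatment. A plan should not need to be read generously on this.

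The large figures are also an upper bound. Standard medication is not to be changed by the study and psychotropic doses must be stable at entry, so a 0.8 SD shift is unlikely. At the small and mild paths with a p<0.05 screen, the Bayesian criterion at effect 0.90 hardly moves (98% and 97% against 98%). This stands too, and those two cases should carry the weight.

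Finally, efficacy is a secondary goal, each model already fixes its baseline outcome, and screening baseline values does not inflate type I error. All true. None of it justifies choosing covariates by their association with a randomised arm, which is unsound on either reading.

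**Conclusion.** The concern holds and should be fixed. As written, post-treatment values can enter the efficacy models, and a data-driven screen without a threshold decides what does enter.

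The size depends on the reading. If post-treatment values enter under a p<0.05 screen, the likelier small and mild paths cost 0.03 to 0.07 of a 0.90 SD effect and 3 to 7 points of power; the half-mediated case is an upper bound. If only baseline values are screened, the validity of the test is not threatened. The loss is then the precision that fixed prognostic covariates would bring: 1 to 13 points of power (79–90% against 77–78%) for partial r of 0.2 to 0.4.

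Path strengths, thresholds and prognostic strength are assumptions, since the documents give none. The stated power is unaffected, as are the feasibility, acceptability and safety descriptives.

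**What to change.** 1. State that only values measured before randomisation may enter the efficacy models.
2. In Analyses and in Statistics, replace the screen with a list fixed before unblinding: the baseline value of the outcome plus one or two prognostic baseline variables already planned, such as age and baseline MMSE. For the MMSE model, add age only, because its baseline is already in.
3. Report post-treatment clinical and anthropometric data descriptively by arm.
4. Reconcile the paragraph before Table 1 with Table 1 on whether and when these data are collected after treatment.

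The cost is wording. Age and MMSE are already planned at baseline, so no assessment is added and N does not change. The covariates must be named before unblinding, and about 2 points of power are lost (76% against 78%) if they prove non-prognostic.
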